Statistical plan	
 The primary analysis population is the mITT population, which includes all randomized subjects who took at least 1 dose of study drug (excluding subjects who qualified for enrollment solely based on changes in smell or taste). For the primary efficacy endpoint of time to sustained clinical recovery, group sample sizes of approximately 625 subjects in each treatment arm (favipiravir and placebo) will achieve sufficient power to demonstrate a clinically meaningful difference using a two-sided Wilcoxon test at an overall significance level of 0.05. An interim analysis will be performed to assess the safety of the patients, the efficacy endpoint for futility, the efficacy endpoint for treatment effect, and the progress of the trial and any medical consideration required to support patient's health and safety. The nominal alpha of 0.02 and of 0.0369, at the time of interim and final analysis, respectively. A p-value less than 0.02 (interim) or 0.0369 (final) will be considered to be statistically significant. Futility will be concluded at interim on the primary efficacy endpoint if Z-value is smaller than 0.58964 (i.e. p-value is larger than 0.6389). For the viral shedding endpoint of time to undetectable viral shedding, group sample sizes of 275 subjects in each treatment arm will have sufficient power to detect a substantial effect size using a two-sided Wilcoxon test at a significance level of 0.05.

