9.2 Study Procedures

9.2.1 Screening, Baseline, Randomization and Treatment (Day 1)

The following procedures will be performed at the Day 1 in-person visit:

- Confirmation of positive SARS-CoV-2 test result
- Confirm subject meets all inclusion and none of the exclusion criteria
- Review the study with the subject and obtain written informed consent and Health Insurance Portability and Accountability Act of 1996 (HIPAA) authorization, or equivalent in another respective country, as applicable such as *Lei Geral de Proteção de Dados Pessoais (LGPD)* in Brazil
- Register the subject in IWRS to allot a unique subject ID (screening number)
- Randomize subject to treatment arm in IWRS as per randomization schedule
- IWRS to assign unique randomization number to the subject
- IWRS to assign IP kit number as per randomization schedule
- Record demographics (age, race, ethnicity, gender)
- Review and record medical history, surgical history
- Review and record smoking, alcohol and medication history
- Document all current medications, including medications over the counter and herbal medications
- Record height and weight
- Record COVID-19 symptoms for inclusion
- Record confirmation of positive SARS-CoV-2 test result
- Record number of days since onset of symptoms
- Collect blood sample for below listed blood tests:
 - CBC with differential, Electrolytes, BUN, Creatinine, Random Blood Serum Glucose, AST, ALT, Bilirubin, uric acid, SARS-CoV2 IgG, IL-6, IL-10, ESR, CRP, D-Dimer, ferritin. (CRP = C-reactive protein, IL-6 = Interleukin-6, IL-10 = Interleukin-10, CBC = Complete Blood Count).
 - Site do not require to wait for blood test result to randomize subjects.

- Provide the allotted IP kit, the blinded treatment (either favipiravir or placebo), and other study materials to the subject
- Assist the subject in downloading the ePRO app, create ePRO credentials for the subject, train the subject on how to use the ePRO and enter the Day 1 Dose 1 visit data with the subject during the visit to ensure the subject's understanding.
- Until the sub-study enrollment is completed (112 events have been counted), all subjects will be enrolled into the viral shedding sub-study. However, if they choose so, subjects can opt-out of participating in the viral shedding sub-study.

9.2.2 Treatment Day 1 to Day 10

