The unbinding futility rule uses a Power family beta spending function with $\Phi=1.147$ and the probability to stop for futility at interim when there is no difference between the two groups (i.e. $HR=1$) is 73%.

The test for efficacy at interim uses a Power family alpha spending function with $\Phi=1.147$ and if the hazard ratio is truly 1.25, the probability to conclude efficacy at interim is 49%.

This is to be noted that the futility rule is unbinding and that the recommendations whether or not to stop for futility will be done by the Data and Safety Monitoring Board (DSMB) (see section 5.5), upon review of the safety and efficacy data, and not solely based on the futility rule.

10.2.3 Sample Size Determination: Sub-study's Viral Shedding Endpoint: Time to undetectable viral shedding by study day 10

Group sample sizes of approximately 275 subjects in each treatment group (Favipiravir and placebo) in order to obtain 112 undetectable viral shedding events will achieve sufficient power to detect a clinically and epidemiologically meaningful effect size using a two-sided Wilcoxon test at a significance level of 0.05.

10.2.4 Sample Size Justification: Sub-study's Viral Shedding Endpoint: Time to undetectable viral shedding by study day 10

To calculate the required sample size, we used the following assumptions: 1) Follow-up duration per patient of 10 days, 2) Alpha of 0.05, 3) Lost to follow up of 0, 4) Exponential survival rates, 5) Median

time to sustained clinical recovery for the control group of 5 days, 6) Median time to sustained clinical recovery for the favipiravir group of 2.9 days.

In order to detect as statistically significant difference in the median time to undetectable viral shedding of 5 vs. 2.9 days in the control vs. favipiravir group, respectively (HR = 1.7), it is estimated that a total of about 550 subjects (275 per treatment group) in order to obtain 112 clinical events defined as undetectable viral shedding events would be required to achieve a power of 80%.

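### The viral-shedding sub-study's 80% power at 112 events is a log-rank figure; the Wilcoxon test named beside it has about 73–76% power at that count

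*Combined protocol and SAP*

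**What the plan says.** Section 10.2.3 sizes the sub-study at about 275 subjects per arm, for 112 conversions, to give "sufficient power to detect a clinically and epidemiologically meaningful effect size using a two-sided Wilcoxon test at a significance level of 0.05". The statistical plan in the synopsis (2.1) names the same test: "sufficient power to detect a substantial effect size using a two-sided Wilcoxon test at a significance level of 0.05".

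Section 10.2.4 gives the calculation. It assumes "Follow-up duration per patient of 10 days", alpha 0.05, no loss to follow-up and exponential times. Its numbered list labels the two medians as times to clinical recovery, but the next sentence applies them to viral shedding, as "5 vs. 2.9 days in the control vs. favipiravir group, respectively (HR = 1.7"). From these it concludes that about 550 subjects "in order to obtain 112 clinical events defined as undetectable viral shedding events would be required to achieve a power of 80" per cent.

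Section 9.2.1 uses the same count as an operating rule: "Until the sub-study enrollment is completed (112 events have been counted), all subjects will be enrolled into the viral shedding sub-study".

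Section 10.6 names no test for this endpoint and refers only to time-to-event methods. Section 10.4 specifies the Gehan Wilcoxon test, and says that it favours early events, but for time to sustained clinical recovery. The hierarchy in 10.6 covers clinical recovery, broad progression and narrow progression; viral shedding is not in it.

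**The concern.** Exponential times in both arms mean proportional hazards, and under proportional hazards the log-rank test is the efficient choice. A Wilcoxon test gives later events less weight, and the loss grows with the share of subjects who have the event. Here most subjects would convert within the 10 days. An event count from a log-rank formula therefore does not give the same power to a Wilcoxon test, and the plan shows no Wilcoxon calculation or efficiency adjustment.

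Section 4.0 calls this endpoint the sub-study's primary virologic objective. If the analysis were made at about 112 events with the named test, the chance of missing the assumed effect would be about 24–27% rather than 20%. A reader of the final report would also be given a design power that belongs to a different test.

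**Working it through.** **Inputs.** From 10.2.3 and 10.2.4: two-sided alpha 0.05, power 80%, 112 events, medians 5 and 2.9 days, hazard ratio stated as 1.7 (5/2.9 = 1.724), exponential times, 10-day follow-up, no loss. Allocation is 1:1 (7.3).

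**1. Reproducing the 112.**
- Schoenfeld (log-rank): events = 4(1.960 + 0.842)² / (ln HR)². At HR 1.7, 31.40 / 0.2816 = 111.5. At HR 1.724, 31.40 / 0.2967 = 105.8.
- Freedman (log-rank): events = (1.960 + 0.842)² × [(HR + 1)/(HR − 1)]². This gives 116.8 at HR 1.7 and 111.1 at HR 1.724.
- Log-rank power at 112 events and HR 1.7: Φ(0.5306 × √28 − 1.960) = 80.2%.

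Both routes that round up to 112 are log-rank formulas.

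**2. Share converting by Day 10.** Control: 1 − 2^(−10/5) = 75%. Favipiravir: 1 − 2^(−10/2.9) = 91%. The mean is 83%, so 112 events come from about 112/0.829 = 135 evaluable subjects.

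**3. Wilcoxon efficiency.** Take the weight as the pooled proportion not yet converted, which falls from 1 to about 0.17.
- Mean weight = (1 − 0.17²) / (2 × 0.83) = 0.585.
- Mean squared weight = (1 − 0.17³) / (3 × 0.83) = 0.400.
- Efficiency relative to log-rank = 0.585² / 0.400 = 0.856.
- Power at 112 events, HR 1.7: Φ(0.5306 × √(28 × 0.856) − 1.960) = Φ(0.638) = 74%.
- Power at 112 events, HR 1.724: Φ(0.5447 × √(28 × 0.856) − 1.960) = Φ(0.707) = 76%.
- Events for 80%: 111.5/0.856 = 130 at HR 1.7; 105.8/0.856 = 124 at HR 1.724.

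**4. Simulation check.** Exponential times, censoring at Day 10, 136 evaluable subjects:

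| Event times | HR | Mean events | Log-rank | Gehan Wilcoxon |
|---|---|---|---|---|
| Continuous (20,000 replicates) | 1.7 | 112.5 | 80.4% | 73.8% |
| Continuous (20,000) | 1.724 | 112.8 | 82.2% | 75.8% |
| Whole days (12,000) | 1.7 | 112.6 | 80.0% | 73.1% |
| Whole days (12,000) | 1.724 | about 113 | 81.9% | 75.6% |

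The Prentice form of the Wilcoxon test gives nearly the same results. Gehan power is 80.1% at 130.7 events (158 subjects, HR 1.7) and 79.7% at 124.4 events (150 subjects, HR 1.724).

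**5. What follows the trigger.** Subjects already enrolled when the 112th event is counted still complete 10 days. Accrual is not given, so the rates below are assumptions. The ranges cover the two hazard ratios.

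| Evaluable subjects per day | Final events | Gehan power |
|---|---|---|
| *Conversions counted at once (3,000 replicates)* | | |
| 0.5–2 | 113–118 | 73–78% |
| 5 | 126–127 | 79–80% |
| 10 | 141 | 82–83% |
| *Results known only after the Day 5 or Day 10 shipment (2,000 replicates)* | | |
| 1 | 117 | 74–76% |
| 3 | 128 | 79–80% |
| 5 | about 138 | 82–83% |
| 8 | about 154 | 86–88% |

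**The case against.** A reader might infer that the sub-study will be analysed with 73–76% power. The documents do not support that. Section 9.2.1 ends enrolment at 112 counted events and nothing cuts the analysis there. Saliva is shipped only around Days 5 and 10 (7.7.4, 7.7.6), so the count lags and the overrun grows. With fast enough accrual the Wilcoxon test reaches or passes 80%. This part of the objection stands in full. With slow accrual the gap remains, and the plan gives no rate that would settle which case applies.

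The planned 550 subjects also sit uneasily with 112 events. If all 550 were evaluable, the stated medians would give 550 × 0.829 = 456 conversions and over 99% power with either test. The two numbers fit only if about 135/550 = 25% of those enrolled are evaluable. Evaluability does require a positive PCR on Day 1, 2 or 3, but no proportion is given. Conversely, if only about 20% converted by Day 10 (a control median of about 40 days), the tests would nearly coincide: 80.7% for log-rank and 80.6% for Gehan. That contradicts the stated 5-day median, so it does not rescue the power statement.

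The Wilcoxon test is named for this endpoint only in the sample-size text. Section 10.6 leaves the test open, and SAP 3.1, to which the protocol refers for analysis detail, was not available for this review. That is a reason to settle the test. It does not make 112 events, 80% and Wilcoxon consistent in 10.2 and the synopsis.

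**Conclusion.** The point holds as an error in the stated power. The figure of 112 events for 80% is a log-rank result printed beside a two-sided Wilcoxon test. At 112 events the Wilcoxon test has about 73–74% power at the rounded hazard ratio of 1.7 and about 75–76% at the medians themselves, which is 4 to 7 points below the figure printed. It reaches 80% at about 125–131 events. These values rest on section 10.2.4's own assumptions, with about 83% converting by Day 10.

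The power of the final analysis cannot be fixed from the documents, because accrual and the evaluable proportion are not given. Since the endpoint is outside the hierarchy, neither its type I error control nor the labelling claims are affected. The inconsistency is modest, but it should be corrected because it concerns the sub-study's main endpoint and the same count drives an enrolment rule.

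**What to change.** Name the test for the viral-shedding endpoint in 10.6 and make the power statement agree with it, in one of two ways:

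- **Log-rank:** name it in 10.2.3, 10.6 and the synopsis. The 112 events and 80% in 10.2.4 then stand as written.
- **Wilcoxon:** keep it, and restate power at 112 events as about 73–76%, saying which hazard ratio (1.7 or 5/2.9) is meant.

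Either is wording only. The first gives up the emphasis on early conversions; the second prints a less favourable power.

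If sub-study enrolment is still open, an alternative is to keep Wilcoxon and raise the event target and the 9.2.1 trigger to about 125–131. That is 13–19 more conversions, or about 16–23 more evaluable subjects at 83% conversion, which fits within the planned 550 if evaluability permits. Section 13 describes version 3.0 as the last one implemented during the study, so this option may no longer be available.

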10.3 Populations for Analyses

- Modified-Intention-to-Treat (mITT) Analysis Dataset includes all randomized subjects who took at least one dose of study medication (excluding subjects who qualified for enrollment based upon changes in taste and smell). Some of these subjects were included on a previous version of the protocol when the loss of smell or taste was considered as one of the symptoms to be alleviated.
- Modified-Intention-to-Treat 2 (mITT2) Analysis Dataset includes all randomized subjects who took at least one dose of study medication and report (in ePRO) sufficient protocol-mandated COVID-19 symptoms (excluding taste and smell), defined as 2 or more symptoms worse than mild on study day 1. Some of these subjects were included on a previous version of the protocol when the loss of smell or taste was considered as one of the symptoms to be alleviated.
- Intention-to-Treat (ITT) Analysis Dataset includes all randomized subjects.
- Safety Analysis Dataset includes subjects who took at least one dose of study intervention.
- Per-Protocol Analysis Dataset: subset of the subjects in the mITT2 set who took at least 80% of study intervention and had no protocol violations that would affect the primary efficacy endpoint. Such protocol violations include treatment with high dose steroids, remdesivir, or SARS-CoV-2 monoclonal antibodies.
- Other Datasets that may be used for sensitivity analyses

10.4 Statistical Analyses: General Approach

Baseline demographic and clinical characteristics and other results will be summarized using descriptive summary statistics. Data collected in the trial will be summarized overall and by treatment arm.

Survival analysis techniques will be used to analyze the time-to-event variables. Failure curves will be constructed for time to positive event using Kaplan-Meier estimates. Time to sustained clinical recovery will be compared using a Gehan Wilcoxon test which gives more weight to early events. Time to a negative event (such as time to death, time to hospitalization) will be compared using the Log-rank test for comparison of survival distributions. Summary tables for safety and efficacy endpoints will include event rates (Kaplan-Meier estimates of event rates), relative risk, confidence interval for the relative risk, the difference in means/rates, the confidence interval for difference in means/rates, and the p-value.

For categorical variables, results within each arm will be summarized with subject counts, percentages, and 95% confidence intervals. The differences between the two treatment arms will be summarized with the difference in percentages and the asymptotic 95% confidence interval for the difference of two percentages.

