- Proportion of subjects dying from any cause over an assessment period from start of study treatment until Day 28.
- Proportion of subject with COVID-19 progression, where progression is defined as the occurrence at any point from study day 1 to study day 28 of emergency department (ED) visit for any reason OR hospitalization for any reason.
- Proportion of subjects requiring mechanical ventilation over an assessment period from start of study treatment until Day 28.
- Time (number of days) to negative conversion (defined as viral load <100 copies) of detectable SARS-CoV-2 viral RNA (defined as viral load >100 copies) in RT-PCR assays of saliva, from start of study treatment to date of last viral assessment. Included: all subjects with a positive PCR on study day 1 or 2 or 3. The endpoint will be assessed from study day 3 onward.
- Time to Sustained Clinical Recovery defined as number of days from start of study treatment to Sustained Alleviation of Symptoms, evaluated from study day 3 onward.
- Proportion of subjects with COVID-19 progression, where progression is defined as the occurrence from study day 3 onward of any emergency department (ED) visit for COVID-19 worsening or shortness of breath OR hospitalization for COVID-19 worsening or shortness of breath OR death (narrow progression)
- Proportion of subjects with COVID-19 progression, defined as the occurrence from study day 3 onward of any ED visit for COVID worsening or shortness of breath OR hospitalization for COVID worsening or shortness of breath OR death OR the development of symptomatic worsening from study day 3 onward (defined as >2 additional COVID symptoms at a level of moderate or severe which have not existed (at any level of severity) at baseline or fever (temperature of $\geq 38.0^{\circ}\text{C}$) which has not existed at baseline or oxygen desaturation (O2 saturation <94%) which has not existed at baseline) (Broad progression).

Safety Endpoint:

1. Number (and proportion) of patients reporting treatment emergent adverse events (TEAEs) (by MedDRA system organ class and preferred term). See additional information on assessing adverse events under section 9.4.
2. Number (and proportion) of patients reporting serious treatment emergent adverse events (TEAEs) (by MedDRA system organ class and preferred term).
3. Vital Signs including oral temperature, heart rate, oxygen saturation with height and weight.

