10.9 Exploratory Analyses

Exploratory endpoints are related to proportion of subjects and will be presented with counts and percentage. Significance among group will be evaluated using Chi-Square test or Fisher test as applicable. The corresponding confidence interval for the difference in proportions will be calculated.

A detailed description of all statistical analyses is described in the SAP 3.1.

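### Section 10.4 names only an asymptotic interval for differences in percentages; on the usual Wald reading it fails for very rare outcomes such as death or ventilation, so one score-type interval should be named (minor).

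*Combined protocol and SAP*

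**What the plan says.** Section 10.4 sets the general rule: "For categorical variables, results within each arm will be summarized with subject counts, percentages, and 95% confidence intervals". The between-arm comparison is then "the difference in percentages and the asymptotic 95% confidence interval for the difference of two percentages". No alternative is given for small counts.

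The preceding paragraph of 10.4, which deals with survival methods, adds: "Summary tables for safety and efficacy endpoints will include event rates (Kaplan-Meier estimates of event rates), relative risk, confidence interval for the relative risk", followed by "the difference in means/rates, the confidence interval for difference in means/rates, and the p-value". That sentence names no interval method.

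Several outcomes in section 4.0 are proportions that may be very small in outpatients not requiring hospitalization:
- "Proportion of subjects dying from any cause over an assessment period from start of study treatment until Day 28"
- the share of subjects who need a ventilator, counted over the same 28 days
- "Number (and proportion) of patients reporting treatment emergent adverse events (TEAEs) (by MedDRA system organ class and preferred term"), with a matching endpoint for serious events.

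For exploratory proportions, section 10.9 allows a chi-square or Fisher test as applicable and then says: "The corresponding confidence interval for the difference in proportions will be calculated". Section 10.6 uses much the same wording for the progression endpoints. Section 10.7 (safety) names no interval. Sections 10.6.1, 10.8 and 10.9 refer to SAP 3.1 for detail, and its text was not supplied. Within the supplied documents, 10.4 is therefore the only place that says how an interval for a difference in percentages is calculated.

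**The concern.** The asymptotic interval for a difference in percentages is usually the Wald interval. It estimates the standard error from the observed proportions, so an arm with no events contributes no uncertainty at all. The plan foresees sparse tables when it chooses the test, because Fisher is available, but it provides nothing comparable for the interval.

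For death, ventilation or a rare serious adverse event, the interval is how a reader judges how large a harm or benefit the trial has excluded. An interval of zero width, or one that covers well below 95%, overstates what has been ruled out.

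**Working it through.** The documents give no interval width or coverage for these outcomes, so there is no stated figure to reproduce.

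**Inputs.** 625 per arm (10.2.1), 1:1 allocation (5.1), 95% level (10.4), z = 1.96. True event rates are assumptions, shown as a range.

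**Wald formula.** d ± 1.96 × √[p1(1−p1)/n + p2(1−p2)/n], where d = p1 − p2.

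**No event in either arm (0/625 v 0/625).** Both variance terms are 0, so Wald gives (0, 0). For comparison, the Wilson upper limit for 0/625 is z²/(n + z²) = 3.84/628.84 = 0.0061, so the Newcombe interval for the difference is ±0.61 points. Miettinen-Nurminen also gives ±0.61. This result needs no assumed rate. How often it would arise does: the probability of no event in 1,250 subjects is (1 − p)^1250, which is 53.5% at a common rate of 0.05%, 28.6% at 0.1% and 8.2% at 0.2%.

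**One empty arm (0/625 v 2/625).** p2 = 0.0032; standard error = √(0.0032 × 0.9968/625) = 0.00226; 1.96 × 0.00226 = 0.00443. Wald is −0.32 ± 0.44, that is (−0.76, 0.12) points. Miettinen-Nurminen gives (−1.16, 0.29).

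**Coverage.** The two binomial distributions were enumerated in full at 625 per arm, adding the probability of every pair of counts whose interval contains the true difference.

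| Assumed true rates | Wald | Newcombe |
|---|---|---|
| 0.05% v 0.2% | 77.8% | 99.9% |
| 0.1% v 0.3% | 84.5% | 99.8% |
| 0.1% v 0.4% | 91.5% | 99.5% |
| 0.05% v 0.5% | 91.6% | 99.5% |
| 0.1% v 0.5% | 93.5% | 98.5% |
| 1% v 2% | 95.1% | 95.7% |
| 3% v 5% | 94.9% | 95.2% |
| 0.1% v 0.1% | 99.6% | 99.9% |
| 0.2% v 0.2% | 97.8% | 99.5% |
| 0.5% v 0.5% | 95.4% | 96.9% |

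The large shortfalls need rates that differ and are both below roughly 0.4%. A shortfall of a few points remains when the higher rate is 0.5%. The lowest Wald coverage on a grid from 0.05% to 2% was 60.8%, at 0.05% v 0.1%.

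**Choice of replacement (4/625 v 0/625).** Wald is (+0.01, +1.27) points, Miettinen-Nurminen (+0.03, +1.63) and Newcombe (−0.09, +1.63); Fisher p = 0.124. The two score-type methods disagree about zero.

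**The case against.** The strongest reply is that the plan never says Wald. Score intervals are asymptotic too, so a score interval would already satisfy the wording. Further, death and ventilation are exploratory endpoints under 10.9, where the corresponding interval could fairly be read as one matched to whichever test is used; 10.7 promises no interval for adverse events; and SAP 3.1 may settle the matter. All of this stands. A reader might infer that the plan prescribes a Wald interval for every difference, but the documents do not go that far. They leave the method open, with Wald as the usual reading.

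A reader might also infer that these intervals are always too narrow. They are not: with equal true rates Wald covers 95.4% or more at every common rate tabulated. Nor is the relative risk undefined whenever one arm is empty. Taking it as favipiravir over placebo, it is 0 if only the favipiravir arm has no event and undefined only if the placebo arm has none.

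The zero-width case also has limited reach. An adverse event term reported in neither arm would normally not appear in a table, so the case concerns prespecified outcomes such as death and ventilation, where zero counts beside a (0, 0) interval would look visibly degenerate. Finally, a score interval will not always agree with Fisher, as the 4 v 0 example shows, so agreement with the test is not the argument for changing.

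What survives is that the only interval method named has no sparse-count provision, and that its usual reading gives a misleading answer for the rarest outcomes.

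**Conclusion.** The point holds as a minor one. On the Wald reading, the interval collapses to (0, 0) when neither arm has an event, where a score interval gives about ±0.61 points. Its coverage falls to 77.8% or 84.5% at the two lowest unequal rate pairs tabulated. The collapse follows from the formula alone; the coverage figures rest on assumed rates, 625 per arm and the Wald reading, and SAP 3.1 could specify something else.

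The consequence is limited to rare exploratory and safety outcomes. A reader might extend it to the efficacy claims, but the primary analysis is a Gehan-Wilcoxon test and the progression endpoints in the hierarchy are tested by chi-square or Fisher, so no confirmatory decision uses this interval. Where both rates are 1% or more, the interval itself performs adequately.

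**What to change.** In 10.4, replace the word asymptotic with one named score-type interval for all differences in percentages, and refer to it from 10.6 and 10.9. Either Newcombe or Miettinen-Nurminen would serve, but one must be fixed in advance because they can disagree on rare events. Newcombe is conservative at very low rates (98.5% to 99.9% at the unequal pairs tabulated with rates of 0.5% or below). Specify Wilson or exact intervals within arms. Show the relative risk as not estimable when the placebo arm has no event, and give no log-scale interval when either arm has none. Make SAP 3.1 agree.

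The cost is a few sentences and a standard software option. Intervals for rare outcomes become wider. No test, significance level or sample size changes.
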